APPENDIX A – QUESTIONNAIRES EXPLANATION

Surveys and Questionnaires

During the human subjects testing we will be collecting subjective feedback on the comfort and temperature of the experimental liner as well as quality of life with their current liner. These will include the Dermatology Life Quality Index, the Residual Limb Health section of the Prostheses Evaluation Questionnaire (PEQ), the EuroQoL-5D, and custom questionnaires specific to the experimental liner. Some will be administered before any testing, such as the quality of life surveys regarding their current liner, others will be administered immediately upon the conclusion of each test session such as the custom questionnaires.

Visit #1 – Part #1 – Dermatology Life Quality Index

The Dermatology Life Quality Index (DLQI) is a simple, self-administered, validated questionnaire developed by Finlay and Khan [1] that is designed to measure the health-related quality of life of patients suffering from skin issues.

Visit #1 – Part #2 – Modified Dermatology Life Quality Index

Meulenbelt et. al. [2] has modified the DLQI (mDLQI) to apply on a monthly basis and applied it to amputees. The results of this questionnaire will be compared to the validated DLQI. The questionnaire was modified slightly from Meulenbelt et al. for grammatical errors and to change “amputation stump” to “residual limb” to use more commonly accepted terminology.

Visit #1 – Part #3 – EuroQoL-5D

Another questionnaire we will be using is the EuroQoL-5D (EQ-5D) survey. The EQ-5D is a well-known and widely used health status instrument that was developed by the EuroQoL Group and has remained fundamentally unchanged since it was introduced in the 1990s. The number of studies using the EQ-5D suite of instruments, registered with the EuroQoL Group, totaled over 17,000 by 2015. EQ-5D is designed for self-completion by respondents and is ideally suited for use in surveys, in clinics, and in face-to-face interviews. It is cognitively undemanding and takes only a few minutes to complete. We will be using the EQ-5D as a validated measure of quality of life.

Visit #1 – Part #4 – Residual Limb Health Scale

The fourth measure we will be using is a subscale of the validated Prostheses Evaluation Questionnaire (PEQ) [3]. The PEQ consists of 82 items grouped into nine subscales, each addressing a different aspect of prosthesis wear (pain, satisfaction, comfort, etc.). The PEQ scales are not dependent on each other, so it is reasonable to use only those scales of interest. We will be using the Residual Limb Health section which rates qualities such as in-socket perspiration and skin breakdown of the residual limb. For each scale used, all of the individual questions that make up that scale must be included. The questions refer to the prior 4 weeks and are scored using a visual analog scale (100mm line). There is no total score. A guide gives coding instructions for all questions and groups the questions under different subscales. Each subscale score is computed by excluding any unanswered questions and averaging the answers within each subscale.

Visit #2 & Visit #3 – Part #1 & Part #2 – Individual Liner Questionnaire

The custom individual liner questionnaire was developed to rate the different aspects of the experimental and control liner. This questionnaire will be completed immediately after each activity to rate the liner that was used during that activity.

Visit #2 & Visit #3 – Part #3 – Liner Comparison Questionnaire

The custom liner comparison questionnaire was developed to measure the subject's preference for different criteria between the experimental and standard liner. This questionnaire will be completed at the end of Visit #2 and Visit #3 after the subject has completed both sets of activities.

References

- [1] A. Finlay and G. Khan, "Dermatology Life Quality Index (DLQI)-a simple practical measure for routine clinical use," *Clinical and Experimental Dermatology*, vol. 19, no. 3, pp. 210–216, 1994.
- [2] H. Meulenbelt, J. Geertzen, M. Jonkman, and P. Dijkstra, "Skin Problems of the Stump in Lower-limb Amputees: 2. Influence on Functioning in Daily Life," *Acta Dermato Venereologica*, vol. 91, no. 2, pp. 178–182, 2011.
- [3] D. A. Boone and K. L. Coleman, "Use of the Prosthesis Evaluation Questionnaire (PEQ)," *JPO Journal of Prosthetics and Orthotics*, vol. 18, no. Proceedings, 2006.

APPENDIX B – QUESTIONNAIRES

Moisture Management Liner Effectiveness Questionnaire

Version 1.0

Investigators	[name] Liberating Technologies, Inc. [name] [contact]
Sponsor	U.S. ARMY MEDICAL RESEARCH ACQUISITION ACTIVITY (USAMRAA)
Sponsor Protocol #	
Solutions IRB #	

Subject ID:	
--------------------	--

Visit #1 – Part 1 – Dermatology Life Quality Index

The aim of this questionnaire is to measure how much your skin problem has affected your life **OVER THE LAST WEEK**. Please fill in once circle for each question.

Over the last week:	Not Relevant	Not at all	A Little	A lot	Very Much
	1. how itchy, sore, painful or stinging has your skin been?				
2. how embarrassed or self-conscious have you been because of your skin?					
3. how much has your skin interfered with you going shopping or looking after your home or garden?					
4. how much has your skin influenced the clothes you wear?					
5. how much has your skin affected any social or leisure activities?					
6. how much has your skin made it difficult for you to do any sport?					
7. has your skin prevented you from working or studying?	No 	Yes 			
Not Relevant	Not at all	A Little	A lot	Very Much	
-If "No", over the last week how much has your skin been a problem at work or studying?					
8. how much has your skin created problems with your partner or any of your close friends or relatives?					
9. how much has your skin caused any sexual difficulties?					
10. how much of a problem has the treatment for your skin been, for example by making your home messy, or by taking up time?					

Visit #1 – Part 2 – Modified Dermatology Life Quality Index

The aim of this questionnaire is to measure how much your skin problem has affected your life OVER THE LAST MONTH. Please fill in once circle for each question.

Over the last month:	Not Relevant	Not at all	A Little	A lot	Very Much
1. how itchy, sore, painful, or stinging has the skin been on your residual limb?					
2. how embarrassed or self-conscious have you been because of the skin on your residual limb?					
3. how much has the skin on your residual limb interfered with you going shopping or looking after your home or garden?					
4. how much has the skin on your residual limb interfered with the time you wear your prosthesis usually?					
5. how much has the skin on your residual limb affected any social or leisure activities?					
6. how much has the skin on your residual limb made it difficult for you to do any sport?					
7. how much has the skin on your residual limb been a problem at work or studying?					
8. how much has the skin on your residual limb created problems with your partner or any of your close friends or relatives?					
9. how much has the skin on your residual limb caused any sexual difficulties?					
10. how much of a problem has the treatment for the skin on your residual limb been, for example by making your home messy, or by taking up time?					

Visit #1 – Part 3 – EuroQoL-5D

By placing a tick in one box in each group below, please indicate which statements best describe your health today.

MOBILITY

I have no problems in walking about	
I have slight problems in walking about	
I have moderate problems in walking about	
I have severe problems in walking about	
I am unable to walk about	

SELF-CARE

I have no problems washing or dressing myself	
I have slight problems washing or dressing myself	
I have moderate problems washing or dressing myself	
I have severe problems washing or dressing myself	
I am unable to wash or dress myself	

USUAL ACTIVITIES (e.g. work, study, housework, family or leisure activities)

I have no problems doing my usual activities	
I have slight problems doing my usual activities	
I have moderate problems doing my usual activities	
I have severe problems doing my usual activities	
I am unable to do my usual activities	

PAIN / DISCOMFORT

I have no pain or discomfort	
I have slight pain or discomfort	
I have moderate pain or discomfort	
I have severe pain or discomfort	
I have extreme pain or discomfort	

[figure not shown]
ANXIETY / DEPRESSION

I am not anxious or depressed	
I am slightly anxious or depressed	
I am moderately anxious or depressed	
I am severely anxious or depressed	
I am extremely anxious or depressed	

1. We like to know how is your health today.
2. This scale is marked from 0 to 100.
3. 100 means the best health you can imagine.
0 means the worst health you can imagine.
4. Mark an X on the scale to indicate how is your health today.
5. Now, please note the number you marked on the scale in the box below.

Your Health Today =

The best health
you can imagine

Visit #1 – Part 4 – Residual Limb Health Scale

[figure not shown]
Instructions

As you read each question, remember there is no right or wrong answer. Just think of YOUR OWN OPINION on the topic and make a mark THROUGH the line anywhere along the line from one end to the other to show us your opinion.

If you use different prostheses for different activities, please choose the ONE you use more often and answer all the questions as though you were using that prosthesis.

Example

How important is it to you to have coffee in the morning?

Over the past four weeks, rate your morning coffee.

OR check I haven't drunk coffee in the morning in the past four weeks.

This example shows that the person who answered these questions feels that having coffee in the morning is important to him. He also thinks the coffee he has had lately has not been very good.

If he hadn't drunk any coffee in the last four weeks, he would have put a check by that statement instead of putting a mark on the line between **TERRIBLE** and **EXCELLENT**.

As in this example, make a mark across the line rather than using an X or an O.

Please answer all the questions.

Support for development of the PEQ was provided by the U.S. Department of Veterans Affairs.

[figure not shown]
Visit #1 – Part 4 – Residual Limb Health Scale

These questions are about YOUR PROSTHESIS

[figure not shown]
Q. Over the past four weeks, rate how much you sweat inside your prosthesis (in the sock, liner, socket).

[figure not shown]
R. Over the past four weeks, rate how smelly your prosthesis was at its worst.

S. Over the past four weeks, rate how much of the time your residual limb was swollen to the point of changing the fit of your prosthesis.

T. Over the past four weeks, rate any rash(es) that you got on your residual limb.

OR check I had no rashes on my residual limb in the last month.

U. Over the past four weeks, rate any ingrown hairs (pimples) that were on your residual limb.

QR check: I had no ingrown hairs on my residual limb in the last month.

V. Over the past four weeks, rate any blisters or sores that you got on your residual limb.

QR check I had no blisters or sores on my residual limb in the last month

Visit #2 – Part 1 – Individual Questionnaire

Liner: Control / Experimental

ICE Unit: Off / ON

Fill in the circle that best describes the liner you just walked with:

On a scale from 1-5 please rate:					
1. your comfort while standing with this liner	 1	 2	 3	 4	 5 Excellent
2. your ability to stand with this liner	 1	 2	 3	 4	 5 Excellent
3. your comfort while walking with this liner	 1	 2	 3	 4	 5 Excellent
4. your ability to walk with this liner	 1	 2	 3	 4	 5 Excellent
5. how warm your leg felt while wearing this liner	 1 Cold	 2	 3	 4	 5 Extremely Hot
6. how much you sweat while wearing this liner	 1 Not at All	 2	 3	 4	 5 Extreme Amount
7. how socket suspension felt while walking with this liner	 1 Leg Came Out	 2	 3	 4	 5 No Movement
8. how confident you felt that you would not slip out of this liner	 1 Not at All	 2	 3	 4	 5 Very Confident
9. how you would want a product like this for daily use	 1 Not at All	 2	 3	 4	 5 Very Much

10. Please provide any additional comments you feel might be useful to note:

Visit #2 – Part 2 – Individual Questionnaire

Liner: Control / Experimental

ICE Unit: Off / ON

Fill in the circle that best describes the liner you just walked with:

On a scale from 1-5 please rate:					
1. your comfort while standing with this liner	 1	 2	 3	 4	 5 Excellent
2. your ability to stand with this liner	 1	 2	 3	 4	 5 Excellent
3. your comfort while walking with this liner	 1	 2	 3	 4	 5 Excellent
4. your ability to walk with this liner	 1	 2	 3	 4	 5 Excellent
5. how warm your leg felt while wearing this liner	 1 Cold	 2	 3	 4	 5 Extremely Hot
6. how much you sweat while wearing this liner	 1 Not at All	 2	 3	 4	 5 Extreme Amount
7. how socket suspension felt while walking with this liner	 1 Leg Came Out	 2	 3	 4	 5 No Movement
8. how confident you felt that you would not slip out of this liner	 1 Not at All	 2	 3	 4	 5 Very Confident
9. how you would want a product like this for daily use	 1 Not at All	 2	 3	 4	 5 Very Much

10. Please provide any additional comments you feel might be useful to note:

Visit #2 – Part 3 – Comparison Questionnaire

ICE Unit: Off / ON

As you read through each question, remember there is no right or wrong answer. Just check off which prosthetic liner, if any, you prefer for each criterion listed below. It will be most helpful if you are completely truthful with your answers.

Criteria	Experimental	Control	No Preference
1. Ease of donning and doffing			
2. Ability to stand/walk			
3. Comfort while sitting			
4. Comfort while walking			
5. Comfort while standing			
6. Limb sweating			
7. Overall temperature in the socket			
8. Friction/Skin Comfort			
9. Slipping in socket			
10. Overall comfort			
11. Overall preference			

12. What did you **like** about the experimental liner and/or protocol?

13. What did you **dislike** about the experimental liner and/or protocol?

14. Other comments.

Visit #3 – Part 1 – Individual Questionnaire

Liner: Control / Experimental

ICE Unit: Off / ON

Fill in the circle that best describes the liner you just walked with:

On a scale from 1-5 please rate:					
1. your comfort while standing with this liner	 1	 2	 3	 4	 5 Excellent
2. your ability to stand with this liner	 1	 2	 3	 4	 5 Excellent
3. your comfort while walking with this liner	 1	 2	 3	 4	 5 Excellent
4. your ability to walk with this liner	 1	 2	 3	 4	 5 Excellent
5. how warm your leg felt while wearing this liner	 1 Cold	 2	 3	 4	 5 Extremely Hot
6. how much you sweat while wearing this liner	 1 Not at All	 2	 3	 4	 5 Extreme Amount
7. how socket suspension felt while walking with this liner	 1 Leg Came Out	 2	 3	 4	 5 No Movement
8. how confident you felt that you would not slip out of this liner	 1 Not at All	 2	 3	 4	 5 Very Confident
9. how you would want a product like this for daily use	 1 Not at All	 2	 3	 4	 5 Very Much

10. Please provide any additional comments you feel might be useful to note:

Visit #3 – Part 2 – Individual Questionnaire

Liner: Control / Experimental

ICE Unit: Off / ON

Fill in the circle that best describes the liner you just walked with:

On a scale from 1-5 please rate:					
1. your comfort while standing with this liner	 1	 2	 3	 4	 5 Excellent
2. your ability to stand with this liner	 1	 2	 3	 4	 5 Excellent
3. your comfort while walking with this liner	 1	 2	 3	 4	 5 Excellent
4. your ability to walk with this liner	 1	 2	 3	 4	 5 Excellent
5. how warm your leg felt while wearing this liner	 1 Cold	 2	 3	 4	 5 Extremely Hot
6. how much you sweat while wearing this liner	 1 Not at All	 2	 3	 4	 5 Extreme Amount
7. how socket suspension felt while walking with this liner	 1 Leg Came Out	 2	 3	 4	 5 No Movement
8. how confident you felt that you would not slip out of this liner	 1 Not at All	 2	 3	 4	 5 Very Confident
9. how you would want a product like this for daily use	 1 Not at All	 2	 3	 4	 5 Very Much

10. Please provide any additional comments you feel might be useful to note:

Visit #3 – Part 3 – Comparison Questionnaire

ICE Unit: Off / ON

As you read through each question, remember there is no right or wrong answer. Just check off which prosthetic liner, if any, you prefer for each criterion listed below. It will be most helpful if you are completely truthful with your answers.

Criteria	Experimental	Control	No Preference
1. Ease of donning and doffing			
2. Ability to stand/walk			
3. Comfort while sitting			
4. Comfort while walking			
5. Comfort while standing			
6. Limb sweating			
7. Overall temperature in the socket			
8. Friction/Skin Comfort			
9. Slipping in socket			
10. Overall comfort			
11. Overall preference			

12. What did you **like** about the experimental liner and/or protocol?

13. What did you **dislike** about the experimental liner and/or protocol?

14. Other comments.

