The subject will be asked to do the following tasks, similar to Klute et al. [3]: (1) an initial seated rest for up to 60 minutes to obtain baseline in-socket temperature data; (2) an activity to increase their body temperature, such as walking on a treadmill [2, 3] for up to 30 minutes; (3) a seated rest for up to 60 minutes; and (4) the liner and perspiration will be collected off the limb (with a towel) and weighed for changes. The second condition will begin once baseline temperatures have been reached and the test procedure repeated in the other condition

Throughout the in-lab test sessions, photos and/or videos may be taken to document such things as the location of the sensors on the limb, the temperature gradients across the limb (with a thermal camera), etc. At the end of each condition, subjective feedback on the comfort and temperature regulation of each condition will be obtained via a questionnaire developed during this effort. The participants would fill out the questionnaire rating parameters such as perceived comfort, intra-socket temperature, potential loss of suspension, etc.

This visit will take up to 4 hours.

This visit can be repeated at the subject's volition, if more data is required or if re-testing is needed.

Visit 3: The same tasks as described in Visit 2 will be completed using the same data collection process. The order of conditions (Experimental Liner versus Control Liner, with or without the active cooling ICE unit) will be randomized. The subject will perform in-laboratory testing to determine the effectiveness the ICE unit to cool and reduce moisture generation of a residual limb with an experimental liner as compared to with a standard control prosthetic liner.

We expect to demonstrate that even if the socket doesn't reduce the temperature during walking, it can cool the socket immediately upon cessation of walking, unlike the standard socket that produces the sustained high temperatures observed by Klute, et al. [3] and Huff, et al. [2]. This benefit is expected to increase with the addition of the experimental thermally conductive liner.

This visit will take up to 4 hours.

This visit can be repeated at the subject's volition, if more data is required or if re-testing is needed.

Once all testing is completed, the research participant will complete a questionnaire to describe their opinions on the comfort, look, and functionality of the experimental liner and ICE unit.

8. Study Conduct

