The prosthetic interface used in this study will be fabricated by a Board-Certified Prosthetist, following conventional standardized methods. The “ICE System” is to be incorporated into the socket design with manufacturing techniques similar to those used to integrate commercially-available prosthetic components and add-ons, such as suction valves, shuttle locks, elevated vacuum systems (e.g. Ohio Willow Wood ONE system), etc and used in a prior approved protocol (NEIRB # 120160413/ HRPO Log A-17885.2). The inclusion of the “ICE System” will be such that the structural integrity and functionality of the socket will not be compromised. The socket characteristics will be similar to the subject’s usual socket, monitoring and maintaining acceptable mobility and comfort throughout the testing procedure.

CONTROL LINERS

The control liners tested in this study will either be commercial-off-the-shelf (COTS) products that are approved for the general population or made with only the base silicone of the experimental liners. We have standardized the control liner used for this study in order to eliminate confounding factors of liner material and thickness.

PROSTHETIC SOCKS

The prosthetic socks in this study will be commercial-off-the-shelf (COTS) products that have been identified to work well with the ICE system, for example, the Silosheath gel sock by Silipose.

TEMPERATURE SENSORS

Commercially available temperature sensors, such as thermistors, thermocouples and iButtons, may be used to monitor the temperature of the ICE device as well as the temperature of the residual limb inside the prosthetic socket. The thermistors and thermocouples have been used in the approved protocols for the previous and current studies (NEIRB # 120160413/ HRPO Log A-17885.2). The iButton has been used in O&P clinical practice and research studies to monitor temperatures within O&P devices [15].

HUMIDITY SENSORS

Commercially available humidity sensors, such Sensirion SHT21S, may be used to monitor the humidity of the residual limb inside the prosthetic socket. This humidity sensor has been used in another research study on prosthetic sockets following a similar protocol by Cutti et al. [9].

14. Data Analysis

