The data collected in the laboratory will include limb temperature, ambient temperature, limb humidity, ambient humidity, and moisture generation on the limb. Standard outcomes measures will include: Dermatology Life Quality Index, Modified Dermatology Life Quality Index, the Residual Limb Health section of the Prostheses Evaluation Questionnaire (PEQ), and the EuroQol-5D. Custom questionnaires that were developed to assess the experimental liner and ICE system will also be used.

The primary outcome of this study will assess the effect of the experimental liners on the temperature of the residual limb; however secondary measures include moisture generation and humidity on the residual limb as well as satisfaction with the prosthesis using the above measures. Measures during the experimental liner conditions will be compared to the control conditions both with and without the ICE system being active.

15. References

- [1] J. T. Peery, W. R. Ledoux, and G. K. Klute, "Residual-limb skin temperature in transtibial sockets," *The Journal of Rehabilitation Research and Development*, vol. 42, no. 2, pp. 147–154, 2005.
- [2] E. A. Huff, W. R. Ledoux, J. S. Berge, and G. K. Klute, "Measuring Residual Limb Skin Temperatures at the Skin-Prostheses Interface," *JPO Journal of Prosthetics and Orthotics*, vol. 20, no. 4, pp. 170–173, Oct. 2008.
- [3] G. K. Klute, E. Huff, and W. R. Ledoux, "Does Activity Affect Residual Limb Skin Temperatures?," *Clinical Orthopaedics and Related Research®*, vol. 472, no. 10, pp. 3062–3067, Jun. 2014.
- [4] A. Finlay and G. Khan, "Dermatology Life Quality Index (DLQI)-a simple practical measure for routine clinical use," *Clinical and Experimental Dermatology*, vol. 19, no. 3, pp. 210–216, 1994.
- [5] H. Meulenbelt, J. Geertzen, M. Jonkman, and P. Dijkstra, "Skin Problems of the Stump in Lower-limb Amputees: 2. Influence on Functioning in Daily Life," *Acta Dermato Venereologica*, vol. 91, no. 2, pp. 178–182, 2011.
- [6] D. A. Boone and K. L. Coleman, "Use of the Prostheses Evaluation Questionnaire (PEQ)," *JPO Journal of Prosthetics and Orthotics*, vol. 18, no. Proceedings, 2006.

- [7] M. M. Wernke, R. M. Schroeder, C. T. Kelley, J. A. Denune, and J. M. Colvin, "SmartTemp Prosthetic Liner Significantly Reduces Residual Limb Temperature and Perspiration," *Journal of Prosthetics and Orthotics*, vol. 27, no. 4, pp. 134–139, Oct. 2015.

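### The subject-completed forms show which liner is experimental and ask open likes and dislikes of that liner alone, which can add demand bias to the self-reported secondary measures

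*Protocol*

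**What the plan says.** Appendix B gives the forms for Visits 2 and 3.

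- **Individual forms (Parts 1 and 2 of each visit, four in all).** Each carries the field "Liner: Control / Experimental" next to a field for the ICE unit. The subject is told: "Fill in the circle that best describes the liner you just walked with". Nine items on a 1 to 5 scale and one free-text comment follow, the same whichever liner was worn.
- **Comparison forms (Part 3 of each visit).** The subject is told: "Just check off which prosthetic liner, if any, you prefer for each criterion listed below". The answer columns for the 11 criteria, which end with overall preference, are *Experimental*, *Control* and *No Preference*. Items 12 and 13 ask what was liked and disliked "about the experimental liner and/or protocol". No item asks this of the control liner. Item 14 invites other comments.

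Section 7 adds a questionnaire once all testing is done, in which subjects are "to describe their opinions on the comfort, look, and functionality of the experimental liner and ICE unit".

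Section 14 (Data Analysis) makes limb temperature the primary outcome. Its secondary measures are moisture generation and humidity "as well as satisfaction with the prosthesis using the above measures". The measures it lists include custom forms: "Custom questionnaires that were developed to assess the experimental liner and ICE system will also be used". Appendix A says that the comparison form is there to measure preference between the liners.

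**The concern.** A subject who is shown which product is on trial may lean towards it, without intending to, when asked which is better. The setting makes this plausible. Section 1 says that the liner was developed by two companies; Section 8 puts all testing at the facility of one of them and allows staff of the other to attend. No coded labels and no blinding of subjects to the liner are described.

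At stake is the reading of the self-reported comparison. If the comparison forms favour the experimental liner, part of that could come from the role names in the columns, and nothing in the data would separate it from a real preference. The open items add a smaller asymmetry: structured likes and dislikes are gathered for one liner and not for the other. The forms are fixed in the protocol's own appendix, so this is not a detail left to an analysis plan.

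**Working it through.** **Step 1: what the forms reveal, and where they are asymmetric.**

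| Element (Appendix B) | Shows the liner's role? | Same for both liners? |
|---|---|---|
| Individual forms, liner field | Yes, as a field offering both options | Yes |
| Individual forms, items 1 to 9 and comment item 10 | No | Yes |
| Comparison forms, 11 criteria | Yes, as answer columns | Yes, with *No Preference* offered |
| Comparison forms, items 12 and 13 | Yes, in the wording | No, experimental liner and/or protocol only |
| Comparison forms, item 14 | No | Open to either |

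The possible bias in scored answers therefore comes from the role names, not from the rated items. The asymmetry of content is confined to two free-text items.

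**Step 2: can the labels tell subjects something they do not already know?**

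- Section 7: the experimental liner is fitted at Visit 1, the subject may wear it at home to acclimate, and both liners are tried with the check socket at Visit 2. Many subjects may recognise it.
- Section 13: the control may be a commercial product or "made with only the base silicone of the experimental liners". In the second case the two liners may be harder to tell apart.
- Section 7: each subject receives a standardised control liner of matching thickness, so it need not be the subject's own. Able-bodied subjects have no customary liner to compare with.

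The labels can thus add information for some subjects, chiefly able-bodied subjects and those with a base-silicone control. For others they may add little.

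**Step 3: illustration of scale.** The protocol gives no figure to reproduce: no size for the bias, no test for the preference items, and no alpha or power. The following rests on assumptions.

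Inputs: n = 12 (the target in Section 5) and n = 20 (the maximum number of amputees there, not a stated analysis size). Assumed: a two-sided exact sign test at 0.05 on overall preference, every subject choosing one of the liners, no true preference, and a share p choosing the experimental liner because of the label.

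Formula: P(X ≥ r) = Σ from k = r to n of C(n,k) p^k (1−p)^(n−k), where r is the smallest count with P(X ≥ r) ≤ 0.025 at p = 0.5.

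- n = 12, r = 10, p = 0.5: (66 + 12 + 1)/4096 = 79/4096 = 0.019 (two-sided 0.039).
- n = 12, p = 0.6: 66 × 0.6^10 × 0.4^2 + 12 × 0.6^11 × 0.4 + 0.6^12 = 0.064 + 0.017 + 0.002 = 0.083.
- n = 12, p = 0.7: 66 × 0.7^10 × 0.3^2 + 12 × 0.7^11 × 0.3 + 0.7^12 = 0.168 + 0.071 + 0.014 = 0.253.
- n = 20, r = 15: 0.021 at p = 0.5, 0.126 at p = 0.6 and 0.416 at p = 0.7.

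Under these assumptions, the chance of an apparently significant preference for the experimental liner rises from about 2% to 8% or 25% with 12 subjects, and to 13% or 42% with 20. Each *No Preference* answer would lower the effective n.

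**The case against.** The strongest objection is that the labels change little. Subjects are fitted with the experimental liner at Visit 1, may take it home, and handle both liners at Visit 2. The experimental liner may have channels and contains conductive additives, while the control may be a commercial product. Section 4 even allows an amputee's control condition to be a check socket without a liner, although Section 7 says that all subjects are given one; where there is no control liner, coded names would hide nothing. This stands in large part: neutral labels reduce a cue but do not blind.

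A second objection is that the forms are fairer than they may look. This also stands. The rated items are the same for both liners, *No Preference* is offered, both likes and dislikes are asked for, and the comparison form says that there is no right or wrong answer and asks for truthful ones. Pay is hourly and does not depend on the answers.

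Three stronger readings are tempting and are not supported:

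- *That no feedback on the control liner is collected.* Nine ratings and a comment are collected for it, and 11 criteria compare the two liners.
- *That each rating form is headed with the role of the liner just worn.* The field prints both options and reads as a condition entry. The protocol does not say who marks it or when.
- *That perceived heat, sweat and suspension are named secondary outcomes.* Section 14 names satisfaction; these perceptions enter only as items of the custom questionnaires.

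What remains after the objections is that the role names are shown to the person giving the answer, serve as answer columns for preference, and are not needed there.

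**Conclusion.** The point holds as a minor, low-cost improvement. The forms show the liners' roles to subjects in an unblinded comparison at a developer's site, and items 12 and 13 have no control-liner counterpart. Both can be avoided.

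Only the self-reported satisfaction and preference measures are affected. The primary outcome, limb temperature, is measured by sensors and does not depend on the forms.

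The size is unknown. A reader might take the sign-test figures as an estimate of the bias. They are not: the 60% and 70% shares are assumed, *No Preference* is ignored, and the protocol states no such test. Since subjects may know the liner anyway, a shift could not be attributed to the labels alone. The figures show only that at these sample sizes a moderate lean could pass for a real preference.

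**What to change.** 1. On the Part 1 to 3 forms for Visits 2 and 3, replace the role names with *Liner A / Liner B* or *first / second liner today*. The second option spares the subject from having to remember which liner was A.
2. Have staff record the actual condition on a separate key. If A and B are used, vary the allocation across subjects so that neither letter always means the experimental liner.
3. Replace items 12 and 13 with the same like and dislike questions for each liner, and ask for comments on the protocol separately.

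The cost is small but not nil: revised forms, IRB approval of them, and a decoding step that must be checked so that no liner is misassigned. Procedures, visits and sample size stay the same. The gain is partial where the liner is recognised, and largest for able-bodied subjects and where the control is made of the same base silicone.
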